## 1. SUMMARY

Title	"The Neuro Zti Cochlear Implant System Efficacy and Safety in Adults"
Sponsor	Oticon Medical
Investigator Coordinator	[name] (Canada)
Phase and Design	Multinational, multicenter, prospective, open label, single arm.
Study description	
The new cochlear implant system (CIS) is indicated in individuals with serious hearing disabilities who do not obtain benefit from appropriately fitted hearing aid(s). Cochlear implant surgery is safe, but as with any surgery, possible issues or device related issues may occur. The risk benefit balance is well known in cochlear implantation.
 
The aim is to assess the efficacy and the safety of this new CIS in adults.

Primary objectives	
To demonstrate the efficacy of the new CIS through improvement of speech performance in quiet conditions after CIS implantation.
 
To evaluate the safety of the CIS.

Secondary objectives	
To assess the device effect with speech performance in noise.
 
To show sustainability of the device effect in quiet and in noise in time and after 12 months of use.
 
To assess whether the time of course of the response follow the same tendencies (increase, decrease, slope inversion) in the three languages in quiet and noise conditions.

Primary endpoints	
HINT score in quiet (HINT-Q) at 6 months of device use.
 
Major complications incidence rate at 12 months of device use.

Secondary endpoints	
HINT in noise (HINT-N) scores at 3, 6 and 12 months of device use
 
HINT-Q scores at 3 months and at 12 months,
 
Electrodes impedance at each visits
 
ECAP at each visit

Inclusion & exclusion criteria	
Inclusion:
 
 
- <math>\geq 18</math> y.o.,
 
- Bilateral severe-to-profound sensorineural hearing loss,
 
- Post-lingual deafness
 
- Limited benefit from appropriately fitted hearing aid(s),
 
- Primary implantation,
 
- No anatomic contraindications,
 
- Fluent in local language,
 
 
Exclusion:
 
 
- Medical conditions that contraindicate undergoing surgery,
 
- Psychologically unsuitable,
 
- Unwillingness or inability to comply with all investigational requirements.
 

Investigational medical device	Neuro CIS, with Neuro Zti implant and Neuro One processor

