**c) Difference in the time course of HINT-Q responses across languages**

The FAS including all patients instead of the subset of English speaking patients will be used in these secondary analyses. A mixed model for repeated measures will be fitted using the change from baseline to M3, M6 and M12 in the HINT-Q score as the responses and the following covariates or terms: the visit (M3, M6 and M12, fixed effect), the patient (random effect), the language (fixed effect) and the interaction between visit and language. The variance covariance matrix will be unstructured. If the p value of the interaction is below 0.15 then a signal of potential interaction is detected and the time course of speech performance is possibly dependent upon the language. Regardless the p value of interaction a graph will present the time course of the response for each language.

A series of contrasts will be performed to estimate and test:

1) The difference between languages in the change from baseline at each time point.

The estimate and test at M6 will be the most supportive result.

2) The overall mean change from baseline at each time point. The test against no change will be performed. Results will be easily interpreted in the absence of potential interaction (No significant difference in the time course of response between the 3 languages).

3) The overall difference between M6 and M12 in the change from baseline to assess the sustainability of effect in the overall population. This estimate is interpretable in the absence of interaction between visit and language. In the presence of interaction the difference is not easily interpretable and sustainability will be estimated and tested in the English speaking patients only.

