Occurrence of major complications will be a co-primary endpoint and the presentation of the safety profile (all adverse events reported) will be a secondary objective, mainly descriptive. Incidence rate of minor and major complications will be estimated globally and per categories in order to describe the device safety profile.

Secondary objectives are:

- To establish the time course of the change from baseline of HINT-Q score in English speaking patients and in all patients to assess the efficacy of the device in a dynamic perspective.
- To test the sustainability of the device effect in Quiet conditions (HINT-Q) through the comparison of the scores at month 6 and month 12 in English speaking patients and in all patients in case of absence of significant language effect in the improvement from baseline.
- To assess the performance of the device in noise using HINT-N test in English speaking and in all patients at 3, 6 and 12 months compared to baseline (best-aided condition). The comparison of the score at 6 and 12 months will indicate the sustainability of the effect.
- To evaluate the trend of device efficacy in quiet and noise conditions across English speaking, French speaking and Danish speaking patients. In other words; To verify the homogeneity of the observed device effect across the three languages in quiet and noisy conditions through the comparison of the time course of the response of English speaking, French speaking and Danish speaking patients. The purpose is to know whether the results on the overall population reflect correctly the three sub-populations (languages).

Technical functionalities assessment:

- To assess the time course from baseline of impedance values to check device technical functionality. Mixed model will be used to assess in a dynamic perspective the objective measures evolution.

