### **6.3.3. Homogeneity of HINT-Q results across languages and estimates of effects in the FAS and PPS**

(Refer to table 12)

This analysis will be done on the FAS and replicated in PPS.

A mixed model for repeated measures will be fitted using the change from baseline to Month 3, Month 6 and Month 12 in the HINT-Q score as the responses and the following covariates or terms: the visit (M3, M6 and M12, fixed effect), the patient (random effect), the language (fixed effect) and the interaction between visit and language. The variance covariance matrix will be unstructured.

If the p value of the interaction is below 0.15 then a signal of potential interaction will be detected and the time course of the change from baseline will be possibly dependent upon the language.

If the p value of interaction is above 0.15, an interaction will be still possible due to the poor power of the interaction test, but the magnitude of the difference should be limited. Findings obtained on the three languages combined will provide a better external validity than those obtained on English speaking only. Consequently, the interaction will be interpreted as a measure of the generalizability of the effect across languages.

Regardless the p value of interaction a graph will present the time course of the response for each language and for all languages combined.

A series of contrasts will be performed to estimate and test (table 12):

- The difference between languages in the magnitude of the change from baseline at each time point. The contrast at Month 6 will be of major importance.
- The magnitude of the change from baseline to each time point for the 3 languages combined. The estimate at Month 6 will be the most supportive result.
- The significance (difference from zero) of overall (all languages) change at each time point.
- The overall difference between Month 6 and Month 12 of the change from baseline (all languages combined).
- The visit effect (is there a difference between visits in the change from baseline?)
- In the presence of potential interaction between languages and time then the mean effect of languages will be investigated.

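### SAP 6.3.3 reads generalisability across languages from the visit-by-language interaction, which a constant language gap leaves null; the pooling condition and the HINT-N response are also stated inconsistently

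*SAP*

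**What the plan says.** **Aim.** The protocol summary asks whether the responses "follow the same tendencies (increase, decrease, slope inversion) in the three languages in quiet and noise conditions". SAP 1.2 restates this as homogeneity of the device effect and adds a purpose: "The purpose is to know whether the results on the overall population reflect correctly the three sub-populations (languages").

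**Model.** Protocol 3.6.2.4 c) and SAP 6.3.3 fit the same mixed model to change from baseline at M3, M6 and M12, with visit, language, their interaction and patient. An interaction p-value below 0.15 is a signal. The protocol then says that "the time course of speech performance is possibly dependent upon the language". Item 2 of its contrast list also treats the pooled mean change at each visit as simple to interpret when there is no interaction.

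**SAP reading.** Above 0.15, SAP 6.3.3 allows that an interaction may have been missed, "but the magnitude of the difference should be limited". It continues: "Consequently, the interaction will be interpreted as a measure of the generalizability of the effect across languages". The contrast list includes the language differences at each visit: "The contrast at Month 6 will be of major importance". The last item in the list investigates the mean language effect only if an interaction has been signalled. A by-language graph is planned whatever the p-value.

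**Pooled M6 to M12 comparison.** Protocol 3.6.2.4 c) makes it depend on the interaction: "In the presence of interaction the difference is not easily interpretable and sustainability will be estimated and tested in the English speaking patients only". Protocol 2.4.2, SAP 1.2 and SAP 5.7.3 make it depend on the absence of a language effect. SAP 6.3.3 lists it with no condition: "The overall difference between Month 6 and Month 12 of the change from baseline (all languages combined").

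**HINT-N.** Protocol 3.6.2.4 d) takes change from baseline as the response. SAP 6.3.4 takes the post-implantation score. SAP 5.7.4 and Tables 13 and 14 use change from baseline.

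**The concern.** The response already has baseline subtracted, so the size of the benefit in each language is the level of its curve. The interaction looks only at the shape of the curves. It suits the same-tendencies objective in the protocol. It cannot answer the purpose in SAP 1.2, which concerns whether the pooled size of effect represents each language.

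The report could therefore describe the pooled effect as generalisable on a null interaction while its own M6 contrast shows a language gap. The condition on the last contrast item adds to this, because a constant gap would usually not trigger it.

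The differing conditions for the M6 to M12 comparison mean that the same data could be pooled or restricted to English speakers, depending on which section is followed. If HINT-N is modelled as a raw score with no baseline term, baseline differences between languages enter the language contrasts.

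**Working it through.** **The plan's own figures.** Neither document gives a power or precision figure for the language comparisons. The inputs used here are SD 25 for change from baseline (range 22 to 28), languages of 39/8/8 with a floor of 5 French and 5 Danish (taken as 45/5/5), and 20 points as the clinically pertinent improvement. They come from the protocol summary, Protocol 2.4.1.1 and 3.6.1.4, and SAP 1.2 and 1.3. The same mean and SD support the primary sample size: exact one-sample t power for 50 points is 97.1% with 6 patients and 99.1% with the stated 7.

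**Why a constant gap cancels.** Let m(L,v) be the mean change in language L at visit v. An interaction contrast is

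[m(L,M6) − m(L,M3)] − [m(E,M6) − m(E,M3)].

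If m(L,v) = m(E,v) − d at every visit, this is zero for any d. With English at 45, 50, 50 and another language at 25, 30, 30, both rise by 5 and then by 0. The same d also cancels from M6 minus M12.

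**What pooling can hide.** With English at 50 and both other languages at 20, the pooled mean is (39×50 + 16×20)/55 = 41.3.

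**Simulation assumptions.** SD 25 at all visits, within-patient correlation 0.5 or 0.8, complete data, and the gap in one non-English language. The interaction is tested by the Wilks parallelism test at 0.15. The M6 contrast is English against that language, two-sided 0.05, 52 df. There were at least 10,000 trials per setting, so results are good to about one point.

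- Interaction p > 0.15 in about 84 to 86% of trials at constant gaps of 0, 20 and 40 points.
- Interaction p > 0.15 together with M6 contrast p < 0.05:

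| Constant gap | 39/8/8 | 45/5/5 |
|---|---|---|
| 0 | 3–4% | about 4% |
| 10 | 14–15% | about 11% |
| 20 | 44–46% | 31–33% |

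**The claim that the difference is limited.** Read as a difference in time course, take a true 20-point departure at M6 and M12 only. The interaction p-value still exceeds 0.15 in 36% (correlation 0.5) or 5% (0.8) of trials at 39/8/8, and in 49% or 17% at 45/5/5.

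**Pooling conditions.** No section names the test or level for a language effect, so the rate of disagreement depends on what is assumed. With a constant 20-point gap at 39/8/8, the interaction rule pools and the language-effect rule does not in about 35 to 51% of trials. That range covers a 2-df M6 test and a visit-averaged F test, both at 0.05. At level 0.15 the visit-averaged figure is about 67% (correlation 0.5). In the other direction, suppose one language loses 20 points at M12 only. The language-effect rule (visit-averaged, 0.05) pools and the interaction rule does not in 58% / 86% of trials at 39/8/8 and 45% / 77% at 45/5/5 (correlation 0.5 / 0.8).

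**Precision of the M6 differences.** The 95% half-width is t(52) × SD × √(1/n1 + 1/n2), with t = 2.007 and SD 25:

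- English v one language: 2.007 × 25 × √(1/39 + 1/8) = 19.5 points; for 45 v 5, 23.7.
- French v Danish: 2.007 × 25 × √(1/8 + 1/8) = 25.1 points; for 5 v 5, 31.7.

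Half-widths scale with SD, so at SD 22 to 28 the first is 17.1 to 21.8. Power of the M6 contrast for 20 points is about 52% (39 v 8) or 38% (45 v 5).

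**The case against.** The best defence is that the SAP does not ignore the right quantity. It calls the interaction one measure of generalisability, not the only one. It plans the M6 language contrast, stresses it, and graphs each language regardless. It also concedes that the interaction test has poor power. This stands: a reader might infer that the plan would conceal a language gap or has no analysis able to find one, and the documents do not support that. What remains is that the pre-specified generalisability sentence rests on the interaction, and that the mean language effect is conditional on it.

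A reader might also infer that the SAP alone introduced this logic. It did not. Item 2 of Protocol 3.6.2.4 c) already uses the absence of interaction to vouch for the pooled mean change.

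The rates depend on assumptions. Twenty points is the documents' threshold for improvement from baseline, not an expected language difference, and at 10 points the conflict is much rarer. At correlation 0.8 with 39/8/8, the SAP's remark about a limited difference is reasonable. The cancellation itself needs none of these assumptions.

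On HINT-N, SAP 6.3.4 speaks of replicating the HINT-Q analyses and refers to tables that report change, so it may be loose wording. It still names a different response and should be aligned.

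**Conclusion.** The point holds and is minor. The interaction on change from baseline measures similarity of time course. It cannot measure whether the size of the effect is shared across languages, and a constant gap leaves it above 0.15 in about 85% of trials. The frequency of a contradictory report is illustrative: about 3 to 4% with no gap and up to 44 to 46% with a constant 20-point gap in one language at 39/8/8, under SD 25 and correlation 0.5 to 0.8. The conflicts over the pooling condition and the HINT-N response can be read directly from the text; only how often the pooling rules disagree depends on the language test assumed.

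It would go too far to infer that the efficacy conclusion is at risk. The primary test uses English speakers only, and Protocol 3.6.2.4 limits labelling claims to the primary analysis and treats secondary analyses as supportive. What is affected is the wording of secondary conclusions and the choice of population for sustainability.

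**What to change.** 1. Rest the generalisability statement on all three pairwise M6 language differences with 95% confidence intervals. Call the comparison descriptive: the half-widths (about 20 to 24 points for English against one language, 25 to 32 for French against Danish) are about as large as, or larger than, the 20-point threshold, so a non-significant difference does not show homogeneity. Keep the interaction for similarity of time course, and qualify item 2 of Protocol 3.6.2.4 c) in the same way.
2. Remove the condition from the last contrast item in SAP 6.3.3, so that the language effect is estimated whatever the interaction p-value. Add an interaction row to the model shell of Table 12, which lists only patient, visit and language.
3. Replace the remark that the difference should be limited with the interaction contrasts and their confidence intervals.
4. Use one condition for the pooled M6 to M12 comparison. The interaction, as in Protocol 3.6.2.4 c), is the matching term because a constant gap cancels from M6 minus M12. Align Protocol 2.4.2 and SAP 1.2, 5.7.3 and 6.3.3. Always show the by-language M6 to M12 differences with confidence intervals, since a null interaction is not proof of similarity either.
5. Restore change from baseline as the HINT-N response in SAP 6.3.4.

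The cost is wording, a table row and a few model statements, with no new data or visits. The downside is a more cautious statement about the pooled languages, which is what 5 to 8 patients per non-English language can support.

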Study planning	
Start date: January 2017
 
Inclusion period: 23 months
 
Running period: 14 months (1 month eligibility period + 13 months postoperative follow-up)
 
Completion date: December 2019

Number of subjects planned	39 English-speaking subjects to assess the primary endpoint with additionally 16 non-English (8 Danish and 8 French) speaking

	subjects to assess safety. In case of shortage of recruitment in a given language recruitment can be increased in another language provided that a minimum of 5 French and 5 Danish speaking patients should be implanted.
Number of centers	5 in Canada, 1 in Denmark
Statistical analysis	Primary efficacy analysis based on the English speaking patients the primary efficacy endpoint (change from baseline to M6 of the HINT-Q) and a one sample t test. Mixed Model for repeated measures with appropriate contrasts.

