#### **3.5.5.1 Procedures to Assess Efficacy**

For the timing assessments please refer to the schedule of activities in section 3.5.5.4.

Audiometric testing shall be performed by or under the direct supervision of an otolaryngologist, a qualified hearing aid acoustician/specialist, speech-pathologist, technician and/or by an audiologist qualified to perform such tests. The pivotal study should not disrupt the routine follow-up visits of each referral center (i.e. fittings, programming changes, speech therapy, audiology tests, and radiological control).

All subjects will use the same signal processing (e.g. directional microphone) and stimulation strategy (e.g. pulse shape, pulse rate).

All subjects, English and non-English speakers, will be assessed with the same procedure and setups

The Danish (20-sentences-list), the French Canadian (20-sentences-list) and the American English HINT (20-sentences-list) will be used according the local language.

The HINT tests will be conducted with dedicated HINT software.

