## 5. Calibration of speech test software tool in dBA

HINT speech tests are conducted with the help of a dedicated software that facilitates sentences presentation at controlled level and recording of patient's responses. Depending on language, either HINT Pro software or an in-house replica is used.

These tools are calibrated in dBA, and do not use the dB SPL scale for presentation levels (see HINT Pro Operating Instructions). The dBA scale reflects the sensitivity of the human ear at different frequencies and it is used for measures of sound field assessments (Westhorp, 2009).

The dBA scale is the most commonly used one among those defined in the International standard IEC 61672:2003 and in other standards on sound level measurement like ANSI standard ANSI S1.4-1981 (R2006). This scale is applied in order to account for the relative loudness perceived by the human ear, known to be less sensitive to lower frequencies.

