# 1. Overview and study plan

## 1.1. Study Design

This pivotal study is designed as a prospective multi-center, one arm, non-randomized, open label, repeated measures clinical study. The subjects are their own control.

For this pivotal study, 55 patients will be enrolled by 5 centers in Canada and 1 in Denmark.

The Neuro cochlear implant system (CIS) is indicated in individuals with severe-to-profound hearing loss who do not obtain benefit from appropriately fitted hearing aid(s). Cochlear implant surgery is safe, but as with any surgery, possible issues or device related issues may occur. The risk-benefit balance is well known in cochlear implantation.

The aim of this study is to assess the efficacy and the safety of this new CIS in adults.

Device efficacy is defined as an improvement in the speech recognition battery presented at conversational speech levels (60 dB SPL) in quiet after 6 months of use compared to the preoperative condition (best-aided preoperative condition).

Speech perception tests will be conducted

- Preoperatively, on both ear with the best fitted hearing aid(s), and
- Postoperatively, on ipsilateral ear with activated CIS and an occluded contralateral ear with ear-plug.

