### 1.3. Determination of sample size

Sample size determination is based on the two co-primary endpoints: change from baseline to 6 months of the HINT-Q (efficacy assessment), and major complication incidence rate during the 12-month follow-up (safety assessment).

The expected efficacy is an improvement of 50 points at 6 months of device use.

Data on the change from baseline to 6 months are not available in literature, but 2 studies describe the HINT-Q magnitude after 12 months of device use. Waltzman et al. [1] described an increase of 47.7% (SD=26.6%) from pre- to 3 months post-implantation, similar results are reported by Lin et al. [2] with a magnitude of 60% (SD=24.1%) at 12 months. Considering an observed performance plateau around 6 months, we can consider that standard deviation obtained at 3 and 12 months can be used for 6 months of device use in this study. In addition, in the main studies conducted at 6 months, the standard deviation are ranged from 22% to 28%, which is consistent with other results on the change from baseline. Data from literature using the same efficacy assessment criterion provided a weighted average  $\pm$  weighted standard deviation change from baseline of 57.43%  $\pm$  25.05%. Such estimation has been rounded conservatively to 50%  $\pm$  25%.

The sample size required to have 95% chance to get a significant efficacy result assuming a true mean improvement of 50%, a standard deviation of change from baseline of 25% and a type I error of 0.025 (one-sided) is 7 patients. It means that the expected improvement is so large with respect to the variability that the sample size calculation is not driven by efficacy considerations.

As requested by the FDA, the sample size will be set at a total of at least 50 subjects to support the safety. If the incidence rate of major complications is 2% then the chance to observe at least one event is 63.5%. The exact upper limit of the 95% CI will be 10.6% for an observed rate of 2%.

Regarding any complication the expected rate 35%. If the observed rate is 36% then the precision is around 13% in points.

In order to ensure that at least 50 subjects will be implanted with the device, starting with the anesthesia followed by surgery procedure, 55 subjects will be included.

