## 6.5. Site effects analysis

The site effect is partly confounded with the language effect. Consequently, the site effect will be investigated in English speaking patients. An analysis of variance using the change from baseline to M6 as the response and the site as covariate will be performed. If the site effect is significant, then the mean change from baseline to M6 is dependent upon the site. Regardless the p value of ANOVA a Forest plot presenting the mean change from baseline to M6 of each site along with the 95% confidence interval will be presented to verify whether there is just a quantitative difference across sites or a qualitative one (refer to table 12 and the related figure). In case of significant site effect and qualitative difference the site with the largest mean deviation from the overall mean change from baseline will be removed from the sample to estimate the overall mean change from baseline in the remaining sites.

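### The Danish contrasts in SAP 6.3.3 are tested and read as language differences, although the design cannot separate language from centre, country and possibly test software

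*SAP*

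**What the plan says.** - **Model.** SAP 6.3.3 fits the change in HINT-Q at Months 3, 6 and 12 with visit, patient (random), language and visit by language. The model block of mock Table 12 lists patient, visit and language only.
- **Contrasts.** The first contrast to be estimated and tested is "The difference between languages in the magnitude of the change from baseline at each time point", and the one at Month 6 is singled out as the most important. The interaction is to be read as a gauge of how far the effect generalises over languages. SAP 6.3.4 repeats the analysis for HINT-N.
- **Centres.** SAP 1.1: "55 patients will be enrolled by 5 centers in Canada and 1 in Denmark". Protocol 3.4.3, criterion 8, requires fluency in the local language. Protocol 3.5 has the same operators test all patients within a centre.
- **Test system.** Protocol 3.5.5.1: "All subjects, English and non-English speakers, will be assessed with the same procedure and setups". Protocol Appendix 9, section 5: "Depending on language, either HINT Pro software or an in-house replica is used".
- **Caveat.** SAP 6.5: "The site effect is partly confounded with the language effect". Its only consequence there is that the site ANOVA is confined to English speakers. Protocol 3.6.2.4 h says the same.
- **Use of the result.** Under SAP 5.7.3, sustainability is reported across languages if there is no language effect, and otherwise in English speakers only.

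**The concern.** If all Danish speakers come from the Danish centre, a Danish-English difference may reflect language, surgical and fitting practice, the testing staff, the country, or the test software. The model cannot tell these apart, yet the result would carry a p-value labelled as language and an interpretation about generalising over languages. A centre difference could pass for a language effect, or could mask one. Because SAP 5.7.3 depends on the result, such a difference could also change the population in which sustainability is reported.

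**Working it through.** **Inputs from the documents.** SD of change 25 points (SAP 1.3). Planned numbers are 39 English speakers plus "16 non-English (8 Danish and 8 French) speaking" subjects (Protocol 1), with a minimum of 5 each for French and Danish (SAP 1.3). One Danish and five Canadian centres.

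**Inputs assumed, because the documents give none.** Intraclass correlation (ICC) between patients of one centre, 0 to 0.10; 3 to 5 centres enrolling English speakers, with 4 as the central case and equal sizes; Danish speakers enrolled only in Denmark, an inference from the local-language criterion.

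**The plan's own figure.** The SAP asks for "95% chance to get a significant efficacy result assuming a true mean improvement of 50" points, and the number for "a standard deviation of change from baseline of 25% and a type I error of 0.025 (one-sided) is 7 patients". The noncentral t gives 97.1% power at n = 6 and 99.1% at n = 7, so the stated 7 is adequate and one more than needed. No precision or power is stated for the language contrasts.

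**Step 1: is language separable from site?** I checked the rank of a design matrix with intercept, two language columns and five site columns (8 columns).
- French at its own centre: rank 6, and still 6 when the Danish column is deleted.
- French shared with two English-speaking centres: rank 7, and still 7 when the Danish column is deleted.

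In both layouts the Danish column adds nothing once site is in the model. A fixed site term cannot rescue the Danish contrast. It can identify French versus English, but only where centres enrol both.

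**Step 2: standard error without site, Danish minus English at Month 6.**

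SE0 = 25 × √(1/39 + 1/8) = 25 × √0.1506 = 9.70 points; 95% half-width 1.96 × 9.70 = 19.0 points.

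**Step 3: standard error if centres vary.** Partition the variance, with τ² = ICC × 625, kE English-speaking centres and one Danish centre:

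Var = τ² × (1/kE + 1) + (625 − τ²) × (1/39 + 1/8)

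True size of a nominal 5% test = 2 × [1 − Φ(1.96 × SE0 / SE)]

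For ICC 0.05 and kE = 4: τ² = 31.25; Var = 31.25 × 1.25 + 593.75 × 0.1506 = 39.1 + 89.4 = 128.5; SE = 11.34.

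| ICC | SE (points) | SE / SE0 | Half-width | True size |
|---|---|---|---|---|
| 0 | 9.70 | 1.00 | 19.0 | 5.0% |
| 0.01 | 10.05 | 1.04 | 19.7 | 5.8% |
| 0.02 | 10.39 | 1.07 | 20.4 | 6.7% |
| 0.05 | 11.34 | 1.17 | 22.2 | 9.3% |
| 0.10 | 12.76 | 1.32 | 25.0 | 13.6% |

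With 3 to 5 English-speaking centres the SE at ICC 0.10 runs from 12.96 to 12.64. With 45 English and 5 Danish patients (4 centres) it is 11.79 without site, 13.08 at ICC 0.05 and 14.25 at ICC 0.10. A simulation of 20,000 trials gave a size of 9.3% at ICC 0.05 and 14.3% at ICC 0.10 with French at its own centre.

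**Step 4: French versus English.** At ICC 0.05 the simulated size is 9.3% if French speakers have their own centre and 5.6% if they share two English-speaking centres. The documents do not say which applies.

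**The case against.** The other side has several good points.

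- *A homogeneity check does not need attribution.* SAP 1.2 wants to know whether the pooled result represents the three language groups. If Danish patients differ for any reason, pooling is questionable. This stands. A reader might infer that the stated purpose cannot be met, or that the check should be dropped; neither follows. What cannot be supported is the language label and its p-value.
- *The switch in SAP 5.7.3 errs on the safe side.* A false signal leads to English-only reporting, which SAP 6.3.2 provides in any case. In Protocol 3.6.2.4 c the criterion is the visit-by-language interaction, from which a centre effect constant over visits cancels, so the sizes above do not apply to it. This stands too. SAP 5.7.3, however, words the criterion as a language effect, and an effect masked by centre would lead to pooling.
- *The software may not matter.* The second tool is described as a replica, Appendix 9 fixes 60 dBA for all centres and evaluations, and a constant shift largely cancels in a change score. That limits the point, since no particular contrast is shown to be affected. A difference in scale or ceiling would not cancel. Protocol 3.5.5.1 already gives each language its own lists, so its statement on setups need not mean identical software, but the two texts still need reconciling.
- *The analysis is supportive.* Protocol 3.6.2.4 rests labeling claims on the primary analysis, which is confined to English speakers. SAP 6.3.3 also hedges about weak power and possible interaction. This limits the weight of the point without removing it.

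**Conclusion.** The attribution problem holds. Following SAP 6.3.3 as written would produce a Danish-English p-value for language, and a reading about generalising over languages, that a design with one Danish centre cannot support. It rests on the inference that Danish speakers are enrolled only in Denmark.

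A reader might go further and infer that the error bars are too narrow because of the confounding. The documents do not support that. Confounding affects what the contrast means, not its standard error. The standard error is too small only if centres differ, and no between-centre variance is given. SAP 6.5 does plan for a significant site effect, so the possibility is not remote. Under the assumed ICC of 0.01 to 0.10 (39 versus 8 patients, SD 25, 4 English-speaking centres), the standard error should be 4% to 32% larger and the true size is about 6% to 14%; at ICC 0 there is no inflation. Nor is the absent site term a simple oversight for Danish, since a fixed one would be aliased with language.

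For French the effect may be negligible or similar in size, depending on whether centres enrol both languages. No primary, safety or labeling conclusion is affected.

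**What to change.** In SAP 6.3.3, and in the HINT-N replicate in 6.3.4:

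1. Report the Danish-English difference with its confidence interval as a combined language, centre, country and test-system difference, without a p-value for language. Limit the statement on generalising over languages accordingly.
2. Estimate French versus English within the Canadian centres with site in the model where centres enrol both languages. Otherwise state that the contrast is not separable from site.
3. Keep the homogeneity check, but in SAP 5.7.3 report sustainability both in English speakers and in all patients whatever its result, so that a possible centre effect does not switch the reported population.
4. Reconcile Protocol 3.5.5.1 with Appendix 9, section 5, by stating which software each language uses.

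A sensitivity analysis with random site effects over a stated range of ICC could be added to show how far the Danish interval might widen.

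The cost is SAP wording, one model term and a clarification in the protocol. The price in results is a wider interval for French versus English and no language p-value for Danish.
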